5.1.2. Tables

All tables are organized by study part and by treatment, i.e., two treatments on each table: the active dosing regimen and its matching vehicle placebo. All statistical comparisons are between the active dosing regimen vs. its matching vehicle placebo in each study part separately.

	Document Number: CLN.001.SAP	Version: 0
	Document Title: Clinical Study CPN-201 Statistical Analysis Plan	Page 13 of 35

5.1.3. Subject Listings

All supporting data to tables and figures will be sorted and listed by study part, treatment, investigator, subject, and visit.

5.1.4. Reporting Conventions

The information and explanatory notes in the “footer” or bottom of each table and listing will include the following information:

- Date of output generation
- SAS® program name, including the path where the program is stored
- Any other output specific details that require further elaboration
- In general, tables will be formatted with a column displaying findings for all subjects by treatment group in each study part.
- For summary tables, the following reporting convention in [Table D](#) will be used unless otherwise stated:

[Table D](#) Decimal Places

Categorical measures	Counts (n)	None
	Percentages (%)	1 decimal place
Continuous measures	n	None
	Mean	i+1 decimal places
	Median	i+1 decimal places
	SD	i+1 decimal places
	Min	i decimal places
	Max	i decimal places
	p-values	if <0.001: presented as <0.001
		if ≥ 0.001: presented to 3 decimal places

i refers to the number of decimal places reported in the CRF or other appropriate source data for the original data.

5.1.5. Visits, Days, PODs, EOT and EOS

5.1.5.1. Definition of Visits

Based on [Tables C1 and C2](#), Schedule of Events, visits and their nominal days relative to the surgery are further described in [Table E](#) below.

	Document Number: CLN.001.SAP	Version: 0
	Document Title: Clinical Study CPN-201 Statistical Analysis Plan	Page 14 of 35

Table E: Visits

Visit Number	Visit Name	Notes
10	Screening	Days -28 to -1. Baseline for most safety endpoints
20	Surgery	Day 0
30	POD1	Randomization and start of study drug. Baseline for efficacy endpoints
40	POD4	3-5 days post-surgery
50	POD8	7-9 days post-surgery
60	POD15 (Part A only)	14 -16 days post-surgery for Part A
70	End of Treatment (EOT) POD22 (Part A) POD15 (Part B)	1-2 days post last dose of study drug. Part A: 22-23 days post-surgery Part B: 15-16 days post-surgery
80	End of Study (EOS) POD28 (Part A) POD22 (Part B)	6-8 days post the last dose of study drug. Part A: 27-29 days post-surgery. Part B: 20-22 days post-surgery
90	UNSCHEDULED	

Some subjects may discontinue their study drug before the scheduled EOT. Situations like this will be discussed in the following sections.

5.1.5.2 Visit windows

It is expected that all visits should occur according to the protocol schedule described in [Table C1](#) and [Table C2](#), the Schedule of Events; visits outside of this schedule will be addressed as protocol deviations. A new visit variable, AVISIT, will be defined based on the visit date relative to the date of surgery and a windowing strategy described by [Table F](#). AVISIT will only be used for efficacy variables.

Table F: Windowing Strategy:

Surgery	Day 1 post-surgery	2-6 days post-surgery	7-11 days post-surgery	12-18 days post-surgery	19-25 days post-surgery	26+ days post-surgery
Day 0	POD1	POD4	POD8	POD15	POD22	POD28

5.1.6. Missing Data and Data Handling Rules

Incomplete dates, missing visits, missing assessments, and situations for subjects who prematurely discontinued study drug are discussed in the following.

	Document Number: CLN.001.SAP	Version: 0
	Document Title: Clinical Study CPN-201 Statistical Analysis Plan	Page 15 of 35

5.1.6.1. Incomplete dates for birthday, adverse events, and medications

The day of birth date will not be collected in order to protect subjects' privacy. To calculate the age from birth date, the day will be assigned as 1st of the birth month.

For analysis of AEs and medications, a complete date should be established in order to determine whether AEs or medications as occurring during study drug or not. For the purpose of handling partially reported start and stop dates for AEs or medications, the following algorithm will be applied:

Missing start day, but month and year present	If study drug had been taken in the same month and year as the occurrence of the AE/medication, then the start day of the event/medication will be assigned to the day of first dose of study drug. Otherwise the start day will be set to the first day of the month.
Missing start day and month, but year present	If study drug had been taken in the same year as the occurrence of the AE/medication, then the start date of the event/medication will be assigned to the date of first dose of study drug. Otherwise the start day and month will be set to 01 January.
Missing end day and month, but year present	The end day and month will be set to the date of end of study. However, if trial termination year is greater than the year of the event/medication, then the day and month will be set to 31December. In subject data listings, start and stop date of AEs or medication will be displayed as reported.

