5.4. Concomitant Therapy and Rescue Medication

All concomitant medications (prescription and OTC) a subject is receiving at the Screening visit and 90 days prior to the Screening visit and taken throughout the course of the study will be recorded in the subject's source documents as well as in the ConMeds page of the eCRF. Information regarding the duration of treatment (including start and stop dates), dose, frequency, site of dosing (right eye, left eye, both eyes, non-ocular) and the reason why the concomitant medication is being taken will be recorded.

Note: The information on concomitant medications will be used to determine whether a subject is taking or has taken prohibited medications as outlined in Section 5.4.2.

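### The partial-date rule in SAP 5.1.6.1 misplaces starts in a second calendar month of dosing, and moves some pre-study medications onto study drug

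*SAP*

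**What the plan says.** SAP 5.1.6.1 gives its purpose: "a complete date should be established in order to determine whether AEs or medications as occurring during study drug or not". Two rows of its table deal with partial start dates, and both apply to adverse events and medications alike.

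- **Day missing, month and year known.** The condition is "If study drug had been taken in the same month and year as the occurrence of the AE/medication". If it is met, "then the start day of the event/medication will be assigned to the day of first dose of study drug". If not: "Otherwise the start day will be set to the first day of the month".
- **Only the year known.** The condition is "If study drug had been taken in the same year as the occurrence of the AE/medication". If it is met, "then the start date of the event/medication will be assigned to the date of first dose of study drug". If not, the start becomes 1 January of the reported year.

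Neither row checks the imputed start against a recorded stop date or against use already noted at Screening. Protocol 5.4 collects such earlier use: "All concomitant medications (prescription and OTC) a subject is receiving at the Screening visit and 90 days prior to the Screening visit". The section also says that listings show dates as reported. The SAP Appendix of corrections and modifications does not touch this rule.

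**The concern.** The missing-day row is safe only when the reported month is the month of first dose. Dosing lasts 21 days in Part A and 14 in Part B, so it often runs into a second month. Study drug was also taken in that month, so the condition is met and the sensible fallback, the first of the month, is switched off.

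The row then has two readings. It speaks of a start day, and its fallback uses day as a day of the month, so a programmer could keep the reported month and insert the first-dose day number. The other reading is the full first-dose date, which overwrites the month that the site reported. One reading puts the event off drug and the other on drug, and that classification is the rule's stated purpose.

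For medications, the year-only row can date a start after the drug was already in use, or after it had stopped. That bears on its status as prior, concomitant or follow-up.

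**Working it through.** The documents give no figure for this rule, so the check applies it to the calendar.

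**Inputs**

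| | Part A | Part B | Source |
|---|---|---|---|
| First dose | POD1 | POD1 | SAP Table E |
| Last dose | POD21 | POD14 | Protocol 6.2.4 |
| End of on-drug window (last dose + 2 days) | POD23 | POD16 | SAP 5.1.6.2 |
| Latest EOS, scheduled window | POD29 | POD23 | Protocol Tables 2A, 2B |
| Latest EOS if counted from a late EOT (EOT + 7 + 1) | 23 + 8 = POD31 | 16 + 8 = POD24 | Protocol 6.2.6 |

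Assumptions: full-length dosing, and every calendar date equally likely as a first-dose date.

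**How often dosing enters a second month.** In a month of L days, a first dose on day d crosses the month end if d + 20 > L (Part A) or d + 13 > L (Part B). That is 20 or 13 days in every month.

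- Part A: 12 × 20 = 240; 240/366 = 65.6%.
- Part B: 12 × 13 = 156; 156/366 = 42.6%.
- Over all 731 dates of 2019–2020: 480 (65.7%) and 312 (42.7%).

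**Day-number reading.** The same day number one month later is L days after first dose, so the imputed day is POD(1 + L): POD29 after a 28-day February, then POD30, POD31 or POD32.

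- Against the on-drug window: even POD29 is later than POD23 and POD16, so every valid date is off drug in both parts.
- Against EOS in Part B: every valid date is later than POD24.
- Against EOS in Part A, 366-day year: 240 − 6 non-existent = 234 valid dates, of which 20 are POD30, 80 are POD31 and 134 are POD32. All 234 are after POD29, but only 134 are after POD31; 20 + 80 = 100 are not.
- Against EOS in Part A, 2019–2020: of 467 valid dates, 447 are after POD29 and 267 after POD31.
- Non-existent dates: first doses on the 31st of March, May, August and October, and on 30 and 31 January, make 6 in a leap year. Adding 29 January makes 7 in other years.

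**Full-date reading.** Every second-month start moves to POD1, in the month before the one reported.

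**Example, Part A.** Surgery 19 August 2019, first dose 20 August, last dose 9 September, EOS 16 September. An event reported as September 2019 becomes 20 September (POD32) on the first reading and 20 August (POD1) on the second. The first of the reported month would be 1 September (POD13).

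**Year-only medications.** Use the same subject with an illustrative Screening on 1 August 2019; the 90-day look-back then reaches 3 May.

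- A drug with start 2019 and stop 30 June 2019 gets a start of 20 August, 31 + 20 = 51 days after it stopped.
- A drug in use at Screening with start 2019 also gets 20 August, so it appears to begin on study drug.
- A drug with start 2018 gets 1 January 2018 and is correctly placed before the study.

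If dosing crosses New Year (20 first-dose dates a year in Part A, 13 in Part B), a start dated only with the new year moves back to December.

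**The case against.** The strongest reply is that no planned adverse event result changes. That stands. Protocol 8.1 counts any event after dosing begins as treatment-emergent, with no end date, and both readings give a start on or after first dose. SAP 5.6.2 does not split its tables by on or off drug. A reader might infer distorted safety tables; the documents do not support that.

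It can also be said that the full first-dose date is the ordinary meaning of the phrase and a cautious choice, because it keeps the event on drug. That is a fair reading, but it still discards the month that the site reported, and the text does not exclude the other one.

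Three further limits stand:

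- A reader might infer that every day-number imputation falls after the last visit. That is true in Part B. In Part A an EOS as late as POD31 is allowed, and after a 28-day February the imputed POD29 lies inside the scheduled window.
- A reader might infer that a washed-out drug would be reported as prohibited use. Protocol 5.4 bases that judgement on the recorded medication information, and nothing in the documents uses imputed dates for it.
- An event reported in the second month may truly have begun after the on-drug window, so an off-drug result is not wrong in every case. The fault is that the rule returns it regardless.

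The percentages are shares of calendar dates, not of events. Contacts after randomization are about a week apart at most on the nominal schedule, so few adverse events should lack a start day.

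**Conclusion.** The rule is wrong as written, with limited consequences. For about 66% of start dates in Part A and 43% in Part B, dosing reaches a second month in which a missing day is imputed either off drug (POD29 to POD32, or a date that does not exist) or into the wrong month. For medications dated only by a year with dosing, the rule can place the start after known use or after a known stop. It should not be inferred that all year-only medications are affected: starts in earlier years are handled correctly, and many long-standing drugs will be among them.

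What is affected is the on-drug classification that the rule exists to settle, and the prior, concomitant or follow-up status of medications summarized under SAP 6.5 (Table 14.1.5). SAP 6.5 does not define those categories by date, so the effect there depends on the definition programmed. The number of partial dates is not given and is probably small. The correction is still worth making, because the rule fails at its one stated task and the remedy costs very little.

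**What to change.** Reword the two rows of SAP 5.1.6.1:

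- **Day missing:** impute the first-dose date only if the reported month is the month of first dose. If the reported month is later, impute the first day of that month. When dosing reached that month, this gives POD2 to POD21 in Part A or POD2 to POD14 in Part B: in the reported month, on drug, and always a real date. It is a cautious convention, not a claim about the true day.
- **Year only:** apply the same principle, so that the first-dose date is used only if the reported year is the year of first dose.
- **Both rows:** never impute a start after the reported stop date.
- **Medications recorded as in use at or before Screening:** do not impute the first-dose date; treat the start as before first dose. Then classify by the stop date: stopped before first dose is prior only; ongoing or stopped after first dose is prior and concomitant. Calling every drug in use at Screening concomitant would mislabel those properly washed out before surgery.

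The cost is a few lines of SAP text and one programming macro. Study conduct and the efficacy analyses are unaffected.

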5.1.6.2. Missing data, rescue, last observation carried forward (LOCF)

LOCF	The last on study drug assessment is carried forward to impute a later missing value.
On study drug	Subjects are considered as being on study drug when they start their first dose until two days after their last dose of the study drug.

For efficacy analyses of POD1 to POD22 (Part A) and POD1 to POD15 (Part B), LOCF method will be used to impute all assessment values after the subjects that are rescued or early withdrawn and/or have stopped being on study drug to calculate mean, standard deviation, 95% confidence interval, median, Q1, Q3, minimum, and maximum for anterior chamber cell (ACC) count, ACC grade, ACF grade, pain grade, and Best Corrected Visual Acuity.

	Document Number: CLN.001.SAP	Version: 0
	Document Title: Clinical Study CPN-201 Statistical Analysis Plan	Page 16 of 35

Therefore, if a subject has an observed POD1 value for an efficacy endpoint, this subject should have observed or imputed values for the same endpoint through POD1 – POD22 for Part A or POD1-POD15 for Part B. Consequently, to avoid confusion, “POD22” will be used in place of “EOT” for Part A and “POD15” for Part B.

LOCF will not be used for “complete” subjects even if they have stopped study drug earlier than POD21 (Part A) and POD14 (Part B).

LOCF will not be used for safety analyses. For safety endpoints, the total number of subjects in the safety population and the summary statistics of all observed data will be calculated for each active dosing regimen and its matching vehicle placebo group for each visit.

Since the eye exams at Screening and EOS visits are evaluated as safety endpoints, the last non-missing observation from the study-eye at post-surgery PODs will not be carried forward to impute missing values at EOS visit for the Screening vs. EOS analyses.

To be clear, in any cases, EOS measurements will not be modified and Screening measurements will not be carried forward.

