5.1.9. Multiple Assessments at One Time Point

Where multiple assessments are recorded for a particular POD, e.g., ACC counts at the same visit or when two visits fall in the same POD window ([Table F](#)), the mean of the assessments will be calculated and used in any derivation of summary statistics. All observed data will be listed.

Note, for any efficacy endpoint:

If EOS falls in the same POD window ([Table F](#)) with another visit, the assessment obtained from that other visit, while the subject is still on study drug, will be used for the efficacy analyses.

If there are no other assessments in the same POD window ([Table F](#)) while the subject is still on study drug, e.g., within 2 days of the last dose of study drug as defined in 5.1.6.2, the EOS assessment will be used for efficacy analyses.

For any safety categorial endpoint, instead of taking the mean of all assessments within that POD window, the assessment obtained at the latest visit within that POD window will be used for that POD.

EOS assessments will not be modified in any case as mentioned in 5.1.6.2.

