5.3.2. Main analytical approach

The primary and secondary efficacy endpoints analyses will follow the General Consideration described in Section 5.1.

Efficacy analysis will be performed for the ITT population.

The primary efficacy endpoints and the secondary endpoints will be summarized in the same tables, figures, and listings.

Rescue and Early Withdrawal:

Rescue criteria: After randomization

- anterior chamber cells count >30 cells,
- an increase in anterior chamber cell count by > 15 cells from POD1/pre-dose baseline, or
- ≥ 2 grade of increase in ACF from POD1/pre-dose baseline.

For visits POD4 through EOS, the total number of subjects randomized, number of subjects who are still on study drug, and the number of subjects rescued for each reason and for subjects withdrawn early will be summarized in [Table 14.2.1](#) for each active dosing regimen and its matching vehicle placebo.

The denominator of each proportion is the number of subjects being randomized.

	Document Number: CLN.001.SAP	Version: 0
	Document Title: Clinical Study CPN-201 Statistical Analysis Plan	Page 20 of 35

Subjects' rescue and early withdrawn information together with reasons will be presented in [Listing 16.2.6.1](#).

Inflammation and Best Corrected Visual Acuity (BCVA) endpoints:

Both eyes at Screening and End of Study (EOS):

Although the tables for these data are numbered 14.2.xxx and listed with other efficacy endpoint tables, the analyses of parameters for eye exams at Screening and EOS visits, especially, those for the non-study-eye, are primarily considered as safety analyses and, therefore, they will be carried out for the safety population.

ACC count, ACC grade, pain grade, ACF grade, and ETDRS acuity (logMAR score) will be summarized descriptively for Screening and EOS visits for each active dosing regimen and its matching vehicle placebo. The summary statistics include total number of subjects in the safety population, mean, standard deviation, 95% confidence interval, median, Q1, Q3, minimum, and maximum of observed data. See [Tables 14.2.2.1.1-14.2.2.1.4](#), and [14.2.5.1](#).

The distribution of ACC, pain, and ACF grades for each treatment group will be described by the frequency within each grade for Screening and EOS visits. See the top part of [Tables 14.2.3.1 – 14.2.3.3](#).

Last non-missing observation from the other PODs will not be carried forward to impute missing values at EOS visit as discussed in Section 5.1.6.2.

Study eye only:

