ACC count, ACC grade, pain grade, ACF grade, and ETDRS acuity (logMAR score) will be summarized descriptively in [Tables 14.2.2.2.1-14.2.2.2.4](#), and [14.2.5.2](#) for POD1-22 (Part A) and POD1-15 (Part B) by each active dosing regimen and its matching vehicle placebo. LOCF method will be used to impute all assessments after the subject stopped being on study drug to calculate mean, standard deviation, 95% confidence interval, median, Q1, Q3, minimum, and maximum. On study drug is defined in Section 5.1.6.2.

The observed data (without LOCF or any other imputation) when the subjects are still on study drug of above listed endpoints will also be summarized in [Tables 14.2.2.3.1 – 14.2.2.3.4](#), and [14.2.5.3](#). The treatment difference will also be reflected by the number of subjects that are still on study drug. PODs defined by [Table F](#) will be used for calculating the treatment group statistics.

	Document Number: CLN.001.SAP	Version: 0
	Document Title: Clinical Study CPN-201 Statistical Analysis Plan	Page 21 of 35

The same statistics will be calculated for CFB of the same endpoints, with POD1 pre-dose measure as the baseline, in [Tables 14.2.2.4.1-14.2.2.4.4](#), and [14.2.5.4](#). LOCF will be used to impute missing values and all assessments after subjects stopped being on study drug. Statistical comparison between each active dosing regimen and its matching vehicle placebo will be carried out for each visit during POD4 - POD22 (Part A) and POD4 – POD15 (Part B) using t-test and Mann-Whitney non-parametric tests noting that p-values will only be considered descriptive and hypothesis-generating.

These endpoints will also be visually presented in [Figures 14.2.2.1, 14.2.2.2, 14.2.5.1](#), and [14.2.5.2](#).

The distribution of ACC, pain, and ACF over different grades for each treatment will be described by the frequency and proportion of subjects within each grade for each active dosing regimen and its matching vehicle placebo for each visit during POD4 – POD22 (Part A) and POD4 – POD15 (Part B) in the lower part of [Tables 14.2.3.1 – 14.2.3.3](#) without LOCF. The denominator of the proportion is the number of subjects randomized. The treatment difference will also be reflected by the number of subjects that are still on study drug.

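### The SAP's on-study-drug status does not end at rescue, so an examination made within two days of the last dose but under rescue medication can enter the observed-data tables as an on-drug result

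*SAP*

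**What the plan says.** **Status.** SAP 5.1.6.2 treats subjects as on study drug "when they start their first dose until two days after their last dose of the study drug". SAP 5.1.9 relies on the same status when it decides whether an EOS assessment may be used for efficacy; it looks for assessments made "while the subject is still on study drug, e.g., within 2 days of the last dose of study drug as defined in 5.1.6.2". Both rest on dosing dates alone.

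**Use.** For the study eye, SAP 5.3.2 summarises "The observed data (without LOCF or any other imputation) when the subjects are still on study drug" in Tables 14.2.2.3.1–14.2.2.3.4 and 14.2.5.3, with visits assigned by the day windows of Table F. It adds: "The treatment difference will also be reflected by the number of subjects that are still on study drug". Table 14.2.1 sets out the "number of subjects who are still on study drug, and the number of subjects rescued for each reason".

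**LOCF.** SAP 5.1.6.2 uses LOCF to "impute all assessment values after the subjects that are rescued or early withdrawn and/or have stopped being on study drug". SAP 5.3.2 is shorter: "LOCF method will be used to impute all assessments after the subject stopped being on study drug". It also says that the efficacy analyses "will follow the General Consideration described in Section 5.1". Protocol 10.6 carries forward, for ACC, the last observation before the first rescue medication.

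**Follow-up after rescue.** Protocol 6.3 and 9.4.1 stop study drug at rescue and keep the subject in the study for assessments. Tables 5A and 5B require the POD8 assessments after a rescue on PODs 2–5. Protocol 6.2.8 allows unscheduled visits to follow subjects on rescue medication.

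**The concern.** The observed-data tables are meant to show what happened while subjects were on study drug. Their only filter is a status that runs for up to two days after the last dose, and nothing in it excludes a subject who has already started rescue medication. ACC count and grade, pain, flare and visual acuity measured under another anti-inflammatory treatment could therefore be reported as results of APP13007 or of vehicle.

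The number still on study drug is exposed in the same way, and 5.3.2 offers it as a sign of the treatment difference. If status is judged on the examination date, one subject could count as still on study drug at POD8 and also as rescued in Table 14.2.1.

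The two-day allowance is sensible in itself: SAP Table E places the EOT visit one to two days after the last dose, and without the allowance routine EOT values would be lost. What is missing is a stop at rescue.

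**Working it through.** The plan gives no figure here to reproduce. The check is which post-rescue examinations pass the filter.

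**Inputs**
- Status rule (SAP 5.1.6.2): an examination on day *e* is on-drug if *e* − last dose ≤ 2.
- Windows (SAP Table F): POD4 = days 2–6, POD8 = days 7–11, POD15 = days 12–18.
- Post-rescue visits (Protocol Tables 5A and 5B), with the EOT assessments done at the rescue evaluation as Protocol 9.4.1 expects.
- Last dose taken on the rescue day *r* or on the day before. The first is realistic, because both parts include a morning dose.

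**Scheduled visits, last dose on the rescue day**

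| Rescue day *r* | Later examination *e* | Combinations | Smallest *e* − *r* | On-drug |
|---|---|---|---|---|
| 2–5 | POD8 visit, days 7–9 | 4 × 3 = 12 | 7 − 5 = 2 | 1 |
| 2–5 | EOS, days 14–16 | 4 × 3 = 12 | 14 − 5 = 9 | 0 |
| 6–9 | EOS, days 14–16 | 4 × 3 = 12 | 14 − 9 = 5 | 0 |
| 10–16 | EOS, days 21–23 | 7 × 3 = 21 | 21 − 16 = 5 | 0 |
| 17–22 (Part A only) | EOS, days 27–29 | 6 × 3 = 18 | 27 − 22 = 5 | 0 |

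The EOS rows total 12 + 12 + 21 + 18 = 63 combinations in Part A and 45 in Part B; none qualifies. The single qualifying case, the same in each part, is last dose and rescue on POD5 (the POD4 visit held one day late) with the POD8 visit on POD7 (one day early). Day 7 is in the POD8 window and the rescue-day examination is in the POD4 window, so the post-rescue value stands alone at POD8. If the last dose was the day before rescue, the smallest gap in the first row becomes 3 and the count is 0 of 12.

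**Other routes.** These are the only ways into the POD15 window.
- An unscheduled post-rescue visit. With the last dose on the rescue day, 9 day combinations in Part B and 14 in Part A fall in that window; with the last dose the day before, 5 and 7. Where the rescue-day examination lies in the same window, SAP 5.1.9 averages the two.
- A deferred EOT. Tables 5A and 5B give a latest day for it, although 9.4.1 expects it at the rescue evaluation. Example: last dose and rescue on POD13, EOT on POD15, gap 2.

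All of these are day combinations, not probabilities.

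**Size per affected subject**
- Number still on study drug, if judged on the examination date: overstated by 1/21 = 4.8 percentage points of a planned arm, or 1/22 = 4.5 points at the 132 subjects in the SAP Appendix (132/6 = 22).
- Observed mean ACC: if the other subjects in the table average *m* and the post-rescue count is *x*, the mean moves by (*x* − *m*)/*n*. With *n* = 21 and assumed values of *x* from 0 to 30 and *m* from 5 to 15, the range is (0 − 15)/21 = −0.71 to (30 − 5)/21 = +1.19 cells. A smaller *n* gives a larger shift. The documents supply neither *x* nor *m*.

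**The case against.** The strongest reply is that the consequence is slight. One scheduled day combination qualifies, it lands at POD8 rather than at the primary time point, and it affects a supportive table. No formal hypothesis is tested, all p-values are exploratory, and the proportions defined as without rescue medication name rescue themselves. All of this stands and sets the severity.

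A second reply is that SAP 5.3.4.1 judges status at the POD, so a subject last dosed on POD5 would be off drug at nominal POD8. That is a possible reading for the counts. But 5.3.2 assigns observed data by the Table F windows, where day 7 is POD8, and it does not say that the status is judged on the nominal day. The schedule footnotes that describe rescued subjects as withdrawn from treatment do not help either, because every subject who stops treatment keeps the two-day tail.

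A third reply is that Table 14.2.1 shows the on-drug and rescued counts together, and Listing 16.2.6.1 shows each rescued subject. An overlap could be found by inspection, but the means would still be computed by the literal rule.

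A reader might also infer from the short LOCF sentence in 5.3.2 that a post-rescue value is carried to POD15. The documents do not support that. SAP 5.1.6.2 names rescue as a trigger for ACC count, ACC grade, flare, pain and visual acuity; 5.3.2 defers to Section 5.1; and Protocol 10.6 fixes the pre-rescue source for ACC. What remains is wording: 5.3.2 omits rescue, and 5.1.6.2 describes the carried value as the last on-drug assessment.

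**Conclusion.** The gap is in the text and the point holds, at minor severity. Followed literally, SAP 5.1.6.2 and 5.3.2 can label a post-rescue examination as on-drug in the observed-data tables and, if status is taken at the examination date, in the number still on study drug. Among scheduled visits that is 1 of 12 combinations in the PODs 2–5 row, provided a dose was taken on the rescue day; otherwise it is none. No scheduled path reaches POD15 when 9.4.1 is followed. The documents give no rescue rate and no count of unscheduled visits, so neither the frequency nor the direction of any between-arm effect can be stated.

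A reader might infer that, because the SAP Appendix cancelled both sensitivity analyses, these tables are the only summary free of LOCF. That does not follow. The cancelled analyses were a per-protocol subset and alternative uses of the two counts for ACC = 0; neither was defined as a non-LOCF summary of mean ACC. SAP 5.3.2 also gives grade distributions without LOCF at the same visits, and observed means at Screening and EOS.

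**What to change.** In SAP 5.1.6.2, state that for efficacy the on-study-drug status ends at the earlier of two days after the last dose or the first dose of rescue or alternative medication. Where only dates are available, treat the rescue-day evaluation as pre-rescue, since Protocol 9.4.1 places it before rescue medication starts. Apply this to the observed-data filter in 5.3.2, to the counts of subjects still on study drug, and to the rule in 5.1.9. Add rescue to the LOCF trigger in 5.3.2, and state that the value carried forward is the last one before that point. This agrees with Protocol 10.6 for ACC and leaves routine EOT values of subjects who were not rescued untouched.

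The cost is one clause and a few matching phrases. Rescue events and medication start dates are already collected in the eCRF (Protocol 5.4 and 9.4.1), so no visit, assessment or data field is added.
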